**Table 19. General Guidelines for Doxorubicin Dose Reduction due to Neutropenia**

Observation	Management Guidelines
ANC < 1 x 10  cells/L	
 
Doxorubicin not administered; treatment cycle delayed
 

At Re-Treatment: 
 
Grade 3 neutropenic fever/infection has occurred
 
If Grade 4 neutropenia lasting > 1 week has occurred
 
Grade 4 ANC without fever/infection
 
	
 
Reduce doxorubicin dose to 60 mg/m^2
 
Reduce doxorubicin dose to 60 mg/m^2
 
Re-treatment with doxorubicin at full dose at Investigator's discretion with prophylactic G-CSF
 

Second Incidence of either Grade $\geq$ 3 neutropenic fever/infection or Grade 4 neutropenia lasting > 1 week	
 
Reduce doxorubicin dose to 45 mg/m^2
 

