**Table 17. Doxorubicin Dose Modifications**

Dose Level	Doxorubicin Dose
Dose Level 1	75 mg/m 
Dose Level -1	60 mg/m 
Dose Level -2	45 mg/m 

General guidelines for dose modifications in response to observed adverse events in presented in [Table 18](#). In consideration that doxorubicin is being used as a standard of care anti-cancer therapy in the enrollment patient population and based on Investigator and site experience with doxorubicin in the enrolled patient population, alternate dose modifications may be implemented after discussion with the Sponsor Medical Monitor.

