**Table 18. Doxorubicin Dose Modification Guidelines**

Worst Toxicity in Prior Cycle	Doxorubicin Dose for Next Cycle
Febrile neutropenia	
Thrombocytopenia with bleeding	Decrease doxorubicin one dose level
ANC Grade 4 for $\geq$ 7 days	
Cardiotoxicity, including any signs and symptoms of heart failure, greater than 10% decline in LVEF to below the LLN, greater than 20% decline in LVEF from any level, or LVEF $\leq$ 45%	Discontinue doxorubicin Consider initiation of dexrazoxane
Grade 3 organ toxicity	Decrease doxorubicin one dose level
Grade 4 organ toxicity	Discontinue doxorubicin
Hepatic impairment	
Serum bilirubin 1.5 – 3.0 mg/dL	50% dose reduction
Serum bilirubin 3.1 – 5.0 mg/dL	75% dose reduction
Serum bilirubin $>$ 5.0 mg/dL	Discontinue doxorubicin

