### **9.3.3.4. Hematologic Toxicity Related to Doxorubicin Administration**

ASCO guidelines for use of WBC growth factors provide that 'prophylactic use of WBC growth factors for prevention of febrile neutropenia is warranted when the risk of febrile neutropenia is approximately 20% or higher and no other equally effective and safe regimen that does not require CSFs is available. Primary prophylaxis is recommended for the prevention of febrile neutropenia in patients who are at high risk on the basis of age, medical history, disease characteristics, and myelotoxicity of the chemotherapy regimen. The NCCN guidelines for hematopoietic growth factors classify soft tissue sarcoma treated with doxorubicin as an example of disease setting and chemotherapy regimen with a high risk for febrile neutropenia (>20%) and recommends G-CSF prophylaxis for patients with high risk (>20%) of febrile neutropenia.

Thus, all patients receiving TTI-621 in combination with doxorubicin should receive prophylaxis with G-CSFs for prevention of febrile neutropenia associated with doxorubicin. Suggested prophylaxis is pegfilgrastim and discussion with the Sponsor Medical Monitor regarding the specific agent is encouraged.

Doxorubicin will not be administered in Cycles 2 – 6 if the patient's ANC is  $< 1 \times 10^9$  cells/L or if the platelet count is  $< 75 \times 10^9$  cells/L. When necessary, the next treatment cycle should be delayed until the ANC is

$\geq 1 \times 10^9$  cells/L and the platelet count is  $\geq 75 \times 10^9$  cells/L and non-hematologic toxicities have resolved. For patients who experience Grade  $\geq 3$  neutropenic fever or infection or Grade 4 neutropenia without fever lasting more than 1 week, doxorubicin should be reduced to 75% of the starting dose (to approximately 60 mg/m^2). If a patient experiences a second incidence of neutropenic fever or infection or has another episode of Grade 4 neutropenia lasting  $> 1$  week, then a second dose reduction to 45 mg/m^2 should be implemented. Doxorubicin dose reductions for neutropenia are described in [Table 19](#).

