Therapeutic and prophylactic use of G-CSFs will be allowed per current ASCO and NCCN guidelines. For patients with Grade 4 ANC without fever/infection lasting less than one week, re-treatment will be allowed at the Investigator's discretion with the full dose of doxorubicin (75 mg/m^2) with recommended use of G-CSFs per current ASCO guidelines.

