**9.4. Management of Adverse Events not Attributable to a Specific Study Treatment**

Guidelines for managing adverse events when attribution to either TTI-621 or doxorubicin is not possible in the opinion of the Investigator are provided in [Table 21](#). Guidelines for management of treatment emergent thrombocytopenia are provided in Table 22 and Table 23 in [Section 9.5](#). Discussion with the Sponsor Medical Monitor is recommended to ensure homogeneity in adverse event management across all patients to the extent possible.

**Table 21. General Guidelines for Management of Adverse Events when Attribution is not Possible in the Opinion of the Investigator**

Note that guidelines for management of thrombocytopenia are provided in Table 22 and Table 23 in [Section 9.5](#)

Observation	Management Guidelines

Hematologic Toxicity
 
 
Grade <math>\geq</math> 3 neutropenia (ANC <math>< 1 \times 10^9/L</math>)
 
Grade <math>\geq</math> 3 anemia
 
Hemoglobin <math>< 8 \text{ g/dL}</math>
 
 
Non-Hematologic Toxicity
 
Grade <math>\geq</math> 3 events excluding:
 
 
Sub-optimally treated nausea, vomiting, diarrhea
 
Alopecia
 
Transient fatigue of a duration consistent with that associated with doxorubicin treatment (1-2 weeks)
 
Infusion-related reaction in the absence of described prophylaxis
 
Laboratory abnormalities that are asymptomatic and/or judged by the Investigator as not clinically significant for the patient
 
	
First Appearance
 
 
Delay study treatment until recovery to Grade <math>\leq 1</math> or baseline with ANC <math>> 1.0 \times 10^9/L</math>. If no recovery after a delay of <math>> 21</math> days, discontinue all study treatment.
 
Reduce doxorubicin and TTI-621 dose levels by one dose level.
 
 
First Re-Appearance
 
 
Delay study treatment until recovery to Grade <math>\leq 1</math> or baseline. If no recovery after a delay of <math>> 21</math> days, discontinue all study treatment.
 
Reduce doxorubicin and TTI-621 dose levels by one additional dose level.
 
 
Second Re-Appearance
 
 
Discontinue all study treatment.
 

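### Table 19's full-dose doxorubicin row for afebrile Grade 4 neutropenia has no one-week limit, so it overlaps the table's own 60 mg/m² row and conflicts with Section 9.3.3.4 and Table 18

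*Protocol*

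**What the plan says.** The doxorubicin rules for Grade 4 neutropenia are in three places in the protocol.

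- **Section 9.3.3.4, text.** The reduction rule is "Grade 4 neutropenia without fever lasting more than 1 week, doxorubicin should be reduced to 75% of the starting dose", which the section equates with roughly 60 mg/m². A second such episode takes the dose to 45 mg/m². The section then points to Table 19: "Doxorubicin dose reductions for neutropenia are described in" that table. Its last paragraph gives the exception: "For patients with Grade 4 ANC without fever/infection lasting less than one week, re-treatment will be allowed at the Investigator's discretion", at the full 75 mg/m² and with G-CSF recommended.
- **Table 18.** The trigger "ANC Grade 4 for $\geq$ 7 days" is grouped with events whose action is to go down one dose level, which is 60 mg/m² under Table 17.
- **Table 19.** While ANC is below 1 × 10⁹/L the instruction is "Doxorubicin not administered; treatment cycle delayed". At re-treatment, Grade 4 neutropenia of more than one week leads to 60 mg/m², whether or not there was fever. The next row covers Grade 4 ANC without fever or infection, gives no duration, and its action is "Re-treatment with doxorubicin at full dose at Investigator's discretion with prophylactic G-CSF".

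**The concern.** The full-dose row in Table 19 is the tabular form of the exception in the last paragraph of Section 9.3.3.4, but the limit that makes it an exception is missing. As worded, it takes in every afebrile Grade 4 episode, including the prolonged ones that the row above sends to 60 mg/m². The table gives no order of precedence between the two rows.

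This is an operative dosing rule for a cytotoxic drug, in a setting that Section 9.3.3.4 itself describes as carrying a febrile neutropenia risk above 20%. Someone working from Table 19 alone would find both a reduction and a discretionary full dose for a patient who has just had more than a week of Grade 4 neutropenia. With up to 20 centers planned, sites could settle that differently.

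**Working it through.** No statistical figure is involved. The check sets the rules side by side for a patient with afebrile Grade 4 neutropenia, attributed to doxorubicin, whose ANC has since recovered to at least 1 × 10⁹/L and who is due a first re-treatment from 75 mg/m².

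| Duration of Grade 4 ANC | Section 9.3.3.4 | Table 18 | Table 19, reduction row | Table 19, full-dose row |
|---|---|---|---|---|
| Under 1 week | 75 mg/m² allowed | no trigger | no trigger | 75 mg/m² allowed |
| Exactly 7 days | neither reduction nor full dose covers it | one level down (60) | no trigger | 75 mg/m² allowed |
| More than 1 week | about 60 mg/m² | one level down (60) | 60 mg/m² | 75 mg/m² allowed |

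*Under one week:* nothing conflicts.

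*More than one week:* three rules give 60 mg/m². Only the full-dose row of Table 19 permits 75 mg/m².

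*Exactly 7 days:* Table 18 reduces. The triggers in Section 9.3.3.4 and the Table 19 reduction row start only after one week, and the exception in Section 9.3.3.4 stops short of one week. The only rule permitting full dose is again the unlimited row.

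**Is the missing limit an isolated omission?** Statements about Grade 4 neutropenia in the doxorubicin rules that carry a time limit:

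- Table 18: 1
- Section 9.3.3.4, reduction rules for first and second episodes: 2
- Section 9.3.3.4, full-dose exception: 1
- Table 19, reduction rows for first and second episodes: 2

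Total: 1 + 2 + 1 + 2 = 6. Without a limit: the Table 19 full-dose row, 1. So 6 of 7 carry a one-week or 7-day limit, and the one that does not is the permissive one.

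**Size of the dose gap.** 75 − 60 = 15 mg/m²; 15 / 75 = 20%.

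**Extraction.** In Table 19 the three re-treatment conditions pair with three actions and read as complete, so a lost phrase is unlikely. Table 18 is less clean: its action cell is read here as merged across the neighbouring triggers, since going down one level is the only action shown for that group. The over-one-week conflict stands on Section 9.3.3.4 and Table 19 without Table 18.

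**After adding the limit.** Under one week maps to discretionary 75 mg/m² and over one week to 60 mg/m². The two Table 19 rows no longer overlap, and the table agrees with its section.

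**The case against.** The strongest reply is that the intent is clear. The paragraph immediately before Table 19 states the limit in full, and the row is evidently its short form. It follows the over-one-week row, so it is natural to read it as covering what remains. It is also permissive: an investigator who reduces the dose breaks no rule. That is fair as to intent, which can be recovered. But the table does not state that reading, Section 9.3.3.4 sends the reader to the table, and a row permitting full dose does conflict with a rule that the dose should be reduced.

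The scope is narrow, and these limits stand:

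- No row allows dosing until ANC has recovered to at least 1 × 10⁹/L (Table 16, Section 9.3.3.4, Table 19). That governs when to re-treat, not at what dose.
- Where an event cannot be attributed to one agent, Table 21 applies to any Grade 3 or higher neutropenia: "Reduce doxorubicin and TTI-621 dose levels by one dose level". The conflict therefore concerns episodes attributed to doxorubicin.
- All patients should receive G-CSF prophylaxis, and the documents give no frequency for prolonged episodes.

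The protocol also allows departures from the guidelines: "alternate dose modifications may be implemented after discussion with the Sponsor Medical Monitor". That route requires the Medical Monitor, whereas the Table 19 row rests on the Investigator alone, so it does not cure the omission.

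On the 7-day boundary, scheduled hematology in Cycles 1 to 6 is on Days 1 and 8, so exactly 7 days will often be hard to distinguish from slightly more. It is a secondary point, worth settling only because the same lines are being edited.

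**Conclusion.** The concern holds. Table 19 as written permits 75 mg/m² for afebrile Grade 4 neutropenia of any duration, against its own 60 mg/m² row, the text of Section 9.3.3.4 and Table 18. The difference at re-treatment is 20% of the dose. The number of patients affected cannot be derived from the documents.

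The conclusion applies to episodes attributed to doxorubicin, after ANC recovery, lasting more than one week; at exactly 7 days it rests on the merged-cell reading of Table 18 and on the text exception stopping short of one week. No endpoint, sample size, decision rule or analysis set is affected. It should be corrected because it is a live dosing instruction bearing on patient safety.

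**What to change.** In Table 19, limit the row for Grade 4 ANC without fever or infection to episodes lasting less than one week.

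In the same edit, set one boundary for exactly 7 days. Using 7 days or more as the reduction trigger, at its two occurrences in Section 9.3.3.4 and its two in Table 19, would agree with Table 18 and with the under-one-week exception. The sponsor should confirm that this is the intended boundary.

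Optional tidying, with no bearing on this finding: Table 19 refers to Grade 3 neutropenic fever or infection at first occurrence, where the text has Grade 3 or higher. Section 9.3.3.4 also equates 75% of the starting dose with about 60 mg/m², but 0.75 × 75 = 56.25, and 60 / 75 = 80%.

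The cost is one phrase in one table row plus aligned wording at four places in the same section and table. No new procedures are needed.

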### 9.3.3.5. Tumor Lysis Syndrome Related to Doxorubicin Administration

Doxorubicin may induce tumor lysis syndrome in patients with rapidly growing tumors and should be managed according to institutional guidelines.

### 9.3.3.6. Radiation Sensitization and Radiation Recall Related to Doxorubicin Administration

Doxorubicin can increase radiation-induced toxicity to the myocardium, mucosa, skin and liver. Radiation recall, including but not limited to cutaneous and pulmonary toxicity, can occur in patients who receive doxorubicin after prior radiation therapy. Patients should not receive radiation unless there is an urgent or emergent need.

### 9.3.3.7. Management of Infusion-Related Reactions Related to Doxorubicin Administration

Infusion-related reactions will be graded as described in [Table 11](#) in [Section 9.2.3.1](#). Management of infusion-related reactions associated with doxorubicin administration are described in [Table 20](#).

**Table 20. Management of IRR Associated with Doxorubicin Administration**

CTCAE Grade	Management Guidelines
Grade 1 or Grade 2	
 
Slow or stop the infusion rate.
 
Provide appropriate further treatment for infusion-related reaction if clinically-indicated per the site's standard practice.
 
If symptoms resolve, the infusion can be re-started or increased, as tolerated, to the baseline rate.
 
Consider premedications and reduced infusion rate
 

Grade 3 or Grade 4	
 
The infusion should be stopped.
 
Aggressively manage symptoms per the site's standard practice for management of doxorubicin-associated infusion-related reaction.
 
Re-challenge is discouraged, especially if vital symptoms have been affected.
 
Consider de-sensitization if therapy is considered essential and patient and physician concur on treatment goals
 

**9.4. Management of Adverse Events not Attributable to a Specific Study Treatment**

Guidelines for managing adverse events when attribution to either TTI-621 or doxorubicin is not possible in the opinion of the Investigator are provided in [Table 21](#). Guidelines for management of treatment emergent thrombocytopenia are provided in Table 22 and Table 23 in [Section 9.5](#). Discussion with the Sponsor Medical Monitor is recommended to ensure homogeneity in adverse event management across all patients to the extent possible.

**Table 21. General Guidelines for Management of Adverse Events when Attribution is not Possible in the Opinion of the Investigator**

Note that guidelines for management of thrombocytopenia are provided in Table 22 and Table 23 in [Section 9.5](#)

Observation	Management Guidelines

Hematologic Toxicity
 
 
Grade <math>\geq</math> 3 neutropenia (ANC <math>< 1 \times 10^9/L</math>)
 
Grade <math>\geq</math> 3 anemia
 
Hemoglobin <math>< 8 \text{ g/dL}</math>
 
 
Non-Hematologic Toxicity
 
Grade <math>\geq</math> 3 events excluding:
 
 
Sub-optimally treated nausea, vomiting, diarrhea
 
Alopecia
 
Transient fatigue of a duration consistent with that associated with doxorubicin treatment (1-2 weeks)
 
Infusion-related reaction in the absence of described prophylaxis
 
Laboratory abnormalities that are asymptomatic and/or judged by the Investigator as not clinically significant for the patient
 
	
First Appearance
 
 
Delay study treatment until recovery to Grade <math>\leq 1</math> or baseline with ANC <math>> 1.0 \times 10^9/L</math>. If no recovery after a delay of <math>> 21</math> days, discontinue all study treatment.
 
Reduce doxorubicin and TTI-621 dose levels by one dose level.
 
 
First Re-Appearance
 
 
Delay study treatment until recovery to Grade <math>\leq 1</math> or baseline. If no recovery after a delay of <math>> 21</math> days, discontinue all study treatment.
 
Reduce doxorubicin and TTI-621 dose levels by one additional dose level.
 
 
Second Re-Appearance
 
 
Discontinue all study treatment.
 


Hematologic Toxicity
 
 
Grade 1 or Grade 2
 
 
Non-Hematologic Toxicity
 
 
Grade 1 or Grade 2
 
	
 
No treatment delay
 
No change in dose level
 

 Interventional or supportive care may be introduced (e.g., G-CSF for neutropenia)

## 9.5. Guidelines for Management of Thrombocytopenia Assessed as Related to Study Treatment (TTI-621 and/or Doxorubicin)

Guidelines for management of treatment-emergent thrombocytopenia occurring in Cycles 1 – 6 or any cycle when doxorubicin and TTI-621 are administered together are provided in [Table 22](#). Guidelines for management of treatment-emergent thrombocytopenia occurring in Cycles  $\geq 7$  or when TTI-621 is administered as monotherapy are provided in [Table 23](#).

**Table 22. TTI-621 and Doxorubicin Treatment Guidelines Based on Thrombocytopenia Assessed as Related to Study Treatment in Cycles 1-6 (Combination Treatment)**

Platelet Count on Day 8	Management Guidelines
<LLN – $75 \times 10^9/L$	
 
Continue TTI-621 and doxorubicin at same dose
 

$75 \times 10^9 – 50 \times 10^9/L$	
 
Continue TTI-621 and doxorubicin at same dose
 

$50 \times 10^9 – 25 \times 10^9/L$	
 
Omit TTI-621 on Day 8
 
Monitor platelet recovery (CBC twice weekly recommended)
 
Consider platelet transfusion per ASCO guidelines if clinically indicated
 
On Day 1 of next cycle: 
 
if platelets have recovered to <math>\geq 75 \times 10^9/L</math>, initiate cycle with doxorubicin at the same dose and TTI-621 at one dose level reduction
 
if platelets have not recovered to <math>\geq 75 \times 10^9/L</math>, hold doxorubicin and TTI-621 and monitor platelets; initiate the cycle when platelets recover to <math>\geq 75 \times 10^9/L</math> with doxorubicin at same dose and TTI-621 at one dose level reduction
 
 
 
In the case of a second occurrence of platelet count decrease to <math><50 \times 10^9</math>, follow the guidelines above or consult with the Sponsor Medical Monitor regarding management
 
The reduced dose of TTI-621 should be used for the remaining combination cycles
 
When the subject completes the combination portion of the study and moves to TTI-621 monotherapy: 
 
the original TTI-621 dose level should be re-instated and platelet counts monitored
 
in the case of platelets <math>< 50 \times 10^9/L</math> without other causality on Day 15, hold TTI-621 until platelets are <math>\geq 50 \times 10^9/L</math> and then continue with TTI-621 at a one dose level reduction
 
on second occurrence of platelets <math>< 50 \times 10^9/L</math> without other causality, reduce TTI-621 by an additional dose level and monitor for tolerability or consult with the sponsor medical monitor regarding management
 
in the absence of disease progression, further dose reductions may be implemented after discussion with the sponsor medical monitor
 
 
 

Platelet Count on Day 8	Management Guidelines
<25 x 10  /L	
 
• Omit TTI-621 on Day 8
 
• Monitor platelet recovery (CBC twice weekly recommended)
 
• Consider platelet transfusion per ASCO guidelines if clinically indicated
 
• On Day 1 of next cycle: 
 
○ if platelets have recovered to <math>\geq 75 \times 10^9/L</math>, reduce doxorubicin and TTI-621 each by one dose level and initiate cycle
 
○ if platelets have not recovered to <math>\geq 75 \times 10^9/L</math>, hold doxorubicin and TTI-621 and monitor platelets; initiate the cycle when platelets recover to <math>\geq 75 \times 10^9/L</math> with doxorubicin and TTI-621 each at one dose level reduction
 
 
 
• In the case of a second occurrence of platelet decrease to <25 x 10^9/L, consult with the Sponsor Medical Monitor regarding management
 
• The reduced dose levels of doxorubicin and TTI-621 should be used for the remaining combination cycles
 
• When the subject completes the combination portion of the study and moves to TTI-621 monotherapy: 
 
○ the original TTI-621 dose level should be re-instated and platelet counts monitored
 
○ in the case of platelets < 50 x 10^9/L on D15, hold TTI-621 until platelets are <math>\geq 50 \times 10^9/L</math> and then continue with TTI-621 at a one dose level reduction
 
○ on second occurrence of platelets < 50 x 10^9/L without other causality, reduce TTI-621 by an additional dose level and monitor for tolerability or consult with the sponsor medical monitor regarding management
 
○ in the absence of disease progression, further dose reductions may be implemented after discussion with the sponsor medical monitor.
 
 
 

Day 8 Platelet Count	Management Guidelines
Any platelet count with clinically-relevant bleeding (more than easily-controlled epistaxis, mild gum bleeding or menses)	
 
• Hold TTI-621 on Day 8
 
• Monitor platelet recovery (CBC twice weekly recommended)
 
• Consider platelet transfusion per ASCO guidelines
 
• On Day 1 of next cycle: 
 
◦ if platelets have recovered to <math>\geq 75 \times 10^9/L</math> and bleeding has resolved, reduce doxorubicin and TTI-621 by one dose level and initiate cycle
 
◦ if platelets have not recovered to <math>\geq 75 \times 10^9/L</math> and/or bleeding has not resolved, hold doxorubicin and TTI-621 and monitor platelets; initiate the cycle when platelets recover to <math>\geq 75 \times 10^9/L</math> with doxorubicin and TTI-621 each at one dose level reduction
 
 
 
• In the case of a second occurrence of platelet count decreased with bleeding attributed to study drug treatment, consult with the sponsor medical monitor regarding management
 
• The reduced dose levels of doxorubicin and TTI-621 should be used for the remaining combination cycles
 
• When the subject completes the combination portion of the study and moves to TTI-621 monotherapy: 
 
◦ the original TTI-621 should be re-instated and platelet counts monitored
 
◦ in the case of platelets <math>< 50 \times 10^9/L</math> on D15, hold TTI-621 until platelets are <math>\geq 50 \times 10^9/L</math> and then continue with TTI-621 at one dose level reduction
 
◦ on Day 1 of the next cycle, if platelet count remains <math>\geq 50 \times 10^9/L</math>, the reduced TTI-621 dose level should be used for the remainder of the subject's participation. If platelet counts do not remain <math>\geq 50 \times 10^9/L</math>, reduce TTI-621 by another dose level and monitor for tolerability.
 
◦ in the absence of disease progression, further dose reductions may be implemented after discussion with the Sponsor Medical Monitor.
 
 
 

**Table 23. TTI-621 Treatment Guidelines based on Thrombocytopenia Assessed as Related to Study Treatment in Cycles  $\geq 7$  (TTI-621 Monotherapy)**

Note that these guidelines are intended to address a patient who has not experienced thrombocytopenia in the combination portion of the study but presents with thrombocytopenia during monotherapy treatment.

Day 15 Platelet Count	Management Guidelines
$<\text{LLN} - 75 \times 10^9/\text{L}$	
 
Continue TTI-621 at same dose
 

$<75 \times 10^9 - 50 \times 10^9/\text{L}$	
 
Continue TTI-621 at same dose
 

$<50 \times 10^9 - 25 \times 10^9/\text{L}$ OR Any platelet count with bleeding attributed to study drug treatment	
 
Monitor platelet recovery (CBC twice weekly recommended)
 
Consider platelet transfusion per ASCO guidelines if clinically indicated
 
Hold TTI-621 until platelets are <math>\geq 50 \times 10^9/\text{L}</math> and then continue with TTI-621 at a one dose level reduction
 
On second occurrence of platelets <math>< 50 \times 10^9/\text{L}</math> without other causality, reduce TTI-621 by an additional dose level and monitor for tolerability; in the absence of disease progression, further dose reductions may be implemented after discussion with the Sponsor Medical Monitor
 

$<25 \times 10^9/\text{L}$	
 
Monitor platelet recovery (CBC twice weekly recommended)
 
Consider platelet transfusion per ASCO guidelines if clinically indicated
 
Hold TTI-621 until platelets are <math>\geq 50 \times 10^9/\text{L}</math> and then continue with TTI-621 at a one dose level reduction.
 
On second occurrence of platelets <math>< 25 \times 10^9/\text{L}</math> without other causality, reduce TTI-621 by an additional dose level and monitor for tolerability or consult with the Sponsor Medical Monitor regarding management. In the absence of disease progression, further dose reductions may be implemented after discussion with the Sponsor Medical Monitor.
 

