**9.2.2. TTI-621 Re-Treatment Guidelines (Initiation of New Cycles of Treatment)**

The parameters described in [Table 9](#) should be met for initiation of a new cycle of treatment with TTI-621. Guidelines for intra-cycle dosing, dosing delays and dosing modifications in response to specific treatment-emergent adverse events are provided in Tables 12, 13, 14, 15, 21, 22 and 23.

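### Table 22's bleeding row contradicts itself on when a new cycle may start, and Table 23's bleeding hold is already satisfied for a patient who bleeds at a platelet count of 50 × 10⁹/L or more

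*Protocol*

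**What the plan says.** Protocol section 9.5 has two tables for thrombocytopenia related to study treatment, and each has an entry for bleeding.

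**Table 22 (Cycles 1–6).** The row is triggered by "Any platelet count with clinically-relevant bleeding (more than easily-controlled epistaxis, mild gum bleeding or menses". TTI-621 is held on Day 8. On Day 1 of the next cycle there are two sub-bullets:
- First: if platelets have reached ≥75 × 10⁹/L "and bleeding has resolved, reduce doxorubicin and TTI-621 by one dose level and initiate cycle".
- Second: if platelets have not reached ≥75 × 10⁹/L "and/or bleeding has not resolved, hold doxorubicin and TTI-621 and monitor platelets; initiate the cycle when platelets recover to" ≥75 × 10⁹/L, with both drugs one level lower.

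**Table 23 (Cycles ≥7).** One row covers both a Day 15 count of <50–25 × 10⁹/L and "Any platelet count with bleeding attributed to study drug treatment". Its instruction is "Hold TTI-621 until platelets are" ≥50 × 10⁹/L "and then continue with TTI-621 at a one dose level reduction". The table opens with a scope limit: "Note that these guidelines are intended to address a patient who has not experienced thrombocytopenia in the combination portion of the study".

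**Related rules.** Section 9.2.2 says that the Table 9 parameters "should be met for initiation of a new cycle of treatment with TTI-621". For intra-cycle dosing and delays it refers to Tables 12–15 and 21–23, without ranking them.

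**The concern.** A hold works only if the condition that ends it can be false when it begins. In both bleeding entries bleeding can start the hold, but only a platelet count ends it. A site that follows the rows literally could resume while bleeding continues. Another site, relying on Table 22's first sub-bullet or on the grade-based tables, would not.

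The situation is foreseeable. Section 13.5.8 lists hemorrhage and thrombocytopenia among the adverse events of special interest. Anticoagulants are allowed (section 8.7.3), as is aspirin up to 325 mg per day (exclusion criterion 12). SAP section 4.3.2 records that Cohort B enrollment stopped after Stage 1 because of Grade 3 or 4 thrombocytopenia on Day 8, so these tables were in active use. Section 9.4 asks for adverse events to be managed alike across patients as far as possible. SAP section 9.1 counts held infusions, delayed cycles and dose reductions, so differing site readings would enter those summaries.

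**Working it through.** The plan gives no figure to reproduce. The check sets each row's entry condition against its release condition.

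**Step 1. Table 22 bleeding row, Day 1 of the next cycle (threshold 75 × 10⁹/L).**

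| Platelets | Bleeding | First sub-bullet | Second sub-bullet | Reading |
|---|---|---|---|---|
| ≥75 | resolved | start | not entered | coherent |
| <75 | resolved | not met | hold, release at ≥75 | coherent |
| <75 | ongoing | not met | hold, release at ≥75 | once the count recovers, the second releases while the first is still not met |
| ≥75 | ongoing | not met | hold, release already true | conflict; the Day 1 hold has no duration |

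The row for counts <25 × 10⁹/L in the same table uses the same hold-and-release wording. It is coherent there because the trigger is a count. In the bleeding row, unresolved bleeding was added to the entry condition but not to the release. That looks like a drafting slip, which is my inference.

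The earlier hold is not affected. TTI-621 is held on Day 8 whatever the count, and the next decision falls on Day 1 of the following 21-day cycle, 22 − 8 = 14 days later.

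**Step 2. Table 23 shared row, Day 15 (threshold 50 × 10⁹/L).**

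| Platelets | Bleeding | Release condition | Reading |
|---|---|---|---|
| <50–25 | no | ≥50 | coherent |
| <50–25 | yes | ≥50 | released on the count whether or not bleeding has stopped |
| ≥50 | yes | ≥50, already true | the hold has no duration |

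For example, a patient bleeding at a count of 60 enters the row through its bleeding entry and satisfies the release at once. What remains is the monitoring, the transfusion prompt and the one-level reduction. The row's recurrence instruction is also tied to a count below 50, so it does not address repeat bleeding at an adequate count.

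**Step 3. Do other rules close the gap?**
- Table 9 requires treatment-related events to be Grade <2 or at baseline, but for starting a new TTI-621 cycle. It bears on Table 22's Day 1 step and does not clearly govern resumption after a Day 15 hold.
- Table 16 allows doxorubicin re-treatment at Grade ≤2. Section 9.3.3.4 is stricter: non-hematologic toxicities are to have resolved before a delayed cycle.
- Table 14 delays TTI-621 for Grade 3 non-hematologic events until the re-treatment criteria are met. Table 15 holds it for intolerable Grade 2 and for Grade 3 events until Grade ≤1 or baseline, and maintains the dose for Grade 1 and tolerable Grade 2. The documents do not say which of these classes hemorrhage belongs to, or which table prevails over Table 23.

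**Step 4. One case through all the rules.** Take an ongoing, clinically relevant, treatment-related Grade 2 bleed, above baseline, with platelets at 90 × 10⁹/L on Day 1 of a combination cycle. Table 22's first sub-bullet does not start the cycle. Its second imposes a hold that is already released. Table 9 bars TTI-621. Table 16's adverse-event criterion does not bar doxorubicin.

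**The case against.** A reader might infer more than the text supports. Four limits stand.

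- **Table 22 is not a count-only rule.** Its first sub-bullet requires resolved bleeding, and its second opens a hold for exactly the patient whose bleeding has not resolved. Only the release clause omits bleeding. Nor is the whole TTI-621 interruption empty, given the Day 8 hold.
- **Not every bleed above the threshold is affected.** Table 9 keeps a treatment-related bleed of Grade 2 or more, above baseline, from a new TTI-621 cycle. Tables 14 and 15 may reach the more severe Day 15 bleeds. Table 23's note excludes patients who had thrombocytopenia during combination treatment. For a patient already on 0.2 mg/kg, Table 10 lists discontinuation as the next step down, so an immediate release need not mean another dose.
- **Tables 22 and 23 do not contradict each other merely by differing.** They cover different regimens, with different thresholds (75 and 50) and different bleeding triggers (clinically relevant, and any attributed bleeding). Table 22's first sub-bullet is not a standard that Table 23 must follow.
- **The background evidence is reassuring.** Section 3.8.1 reports no rise in bleeding risk in earlier TTI-621 experience, and section 8.7.3 provides for adjusting anticoagulant dose in thrombocytopenia. The intravenous study described in section 3.5.2.1 combined TTI-621 with rituximab or nivolumab, not doxorubicin, so this does not settle the question for the present regimen.

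These points narrow the consequence. They do not remove Table 22's internal conflict or give Table 23's hold any effect at a count of 50 or more.

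**Conclusion.** The defect is real and narrow. Table 22's two Day 1 sub-bullets give incompatible answers when bleeding continues at a count of ≥75 × 10⁹/L. Table 23's hold has no duration for a patient within its scope who bleeds at ≥50 × 10⁹/L. Other rules limit the effect only in part, and how they rank against Table 23 is not stated.

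The documents do not support saying that patients will generally be re-dosed during active bleeding. That would need the rows to be applied literally, with no grade-based rule taking precedence and no investigator judgment. They give no bleeding rate for the combination, so the number of patients affected cannot be estimated. No response endpoint or sample-size figure depends on this. It should still be corrected, because a written safety rule that contradicts itself or has no effect invites sites to act differently.

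The conclusion rests on reading each row by its own words and on Table 9 applying to cycle initiation, as section 9.2.2 states.

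**What to change.** Issue a protocol clarification that:

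1. reconciles the two Day 1 sub-bullets of Table 22's bleeding row, so that they take one position on whether bleeding status is a condition for starting the cycle;
2. reconciles Table 23's bleeding entry, so that its hold and release conditions refer to the same trigger;
3. states how both entries relate to Tables 9, 14, 15 and 16 (and to section 9.3.3.4), including which prevails for a Day 15 dose.

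The sponsor sets the clinical content; this review takes no position on it. The cost is two table cells and a sentence on precedence, with no change to the design, sample size or analysis.
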